## 9.7. Genetics

### 9.7.1. Whole Blood Sample for Pharmacogenetic Research

A whole blood sample will be collected for pharmacogenetic analysis as specified in [Appendix 4](#), where local regulations allow.

Samples will not be used to conduct unspecified disease or population genetic research either now or in the future. Samples will be used to investigate variable response to LY3434172 and to investigate genetic variants thought to play a role in cancer. Assessment of variable response may include evaluation of AEs or differences in efficacy.

All samples will be coded with the patient number. These samples and any data generated can be linked back to the patient only by the study site personnel. Samples will be retained at a facility selected by Lilly for a maximum of 15 years after the last patient visit for the study, or for a shorter period if local regulations and/or ERBs/IRBs impose shorter time limits. This retention period enables use of new technologies, response to questions from regulatory agencies, and investigation of variable response that may not be observed until later in the development of LY3434172 or after LY3434172 becomes commercially available.

Molecular technologies are expected to improve during the 15 year storage period and therefore cannot be specifically named. However, existing technologies include whole genome and exome sequencing, genome-wide association studies, multiplex assays, and candidate gene studies. Regardless of the technology utilized, data generated will be used only for the specific research scope described in this section.

## 9.8. Biomarkers

Biomarker research is performed to address questions of relevance to drug disposition, target engagement, pharmacodynamics, mechanism of action, variability of patient response (including safety), and clinical outcome. Sample collection is incorporated into clinical studies to enable examination of these questions through measurement of biomolecules including DNA, RNA, proteins, lipids, and other cellular elements.

As part of Lilly's ongoing efforts to understand the relationship between cancer, genetics, and response to therapy, this study will analyze systemic and tumor tissue-associated biomarkers relevant to LY3434172, mechanism of action of LY3434172, the variable response to study drug(s), immune function, and pathways associated with cancer. These samples may also be used to develop related research methods or to validate diagnostic tools or assays.

Samples for biomarker research will be collected as specified in [Appendix 4](#), where local regulations allow. It is possible that biomarker data for patients in the study has already been generated from samples that were collected and analyzed prior to enrolling in this study. This may include data generated from genetic analyses. If available, these data may be requested from medical records for use in the research described in Sections [9.7.1](#), [9.8.1](#), and [9.8.2](#).

### 9.8.1. *Tissue Samples for Biomarker Research*

Tissue samples for biomarker research will be collected for the purposes described in Section [9.8](#). The following samples for biomarker research will be collected as specified in [Appendix 4](#), where local regulations allow.

Collection of the following tumor tissue sample(s) is **required** for all patients in order to participate in this study.

For patients participating in all cohorts:

- a newly obtained core or excisional pre-treatment biopsy of a tumor lesion from metastatic site **and**
- a tumor tissue sample from a newly obtained core or excisional biopsy specimen collected during the study treatment period as shown in [Appendix 4](#).
- an archival formalin-fixed paraffin-embedded tumor tissue obtained from the primary tumor site, if available and not restricted by local regulations. (Regardless of whether or not the archival tissue is submitted, patients are still required to undergo pretreatment and on-treatment biopsies).

An attempt to obtain up to 4 core-needle biopsies or a surgical biopsy is required, unless medically contraindicated or unsafe and discussed with Lilly CRP/CRS. Optimally, biopsies should be taken from the same metastatic lesion and from areas not previously irradiated (except if the patient had progressed after radiation). For tumor tissue samples that are not archived, the subject has to be willing to undergo baseline and on-study biopsies that should not put subjects at undue risk greater than that which comes with a core biopsy, in other words, a procedure to obtain biopsy should have a serious/severe complication risk no greater than 2%.

If a biopsy does not contain adequate tissue for analysis, the patient may be replaced. Lilly may replace up to 25% patients, if unable to submit an adequate tumor sample.

Collection of the following tumor tissue sample(s) is **optional** for all patients participating in this study:

For patients participating in all cohorts

- a tumor tissue sample from a newly obtained biopsy specimen collected after disease progression or at additional study time points, if warranted and agreed upon by the investigator and Lilly. Such additional biopsies are optional and should be performed only if clinically feasible. If these additional samples are requested, they will be used to further investigate biomarkers that may explain treatment response and resistance mechanisms. If a biopsy is performed after the patient signs the ICF, Lilly may request a tissue sample from the biopsy for additional biomarker testing at any time during the study including post-progression.

Newly acquired tumor biopsies are requested because they provide the most current biomarker characteristics of the tumor compared with biopsies taken at the time of diagnosis (tumor characteristics may shift during subsequent lines of treatment). Pre- and on-treatment assessments are critical to evaluate changes in molecular markers over time and to document any potential immunomodulatory activity of treatment with LY3434172 and should be performed if clinically feasible. Samples will be examined for biomarkers as described in Section 9.8, including but not limited to, PD-L1 expression by immunohistochemistry.

The tissue samples should be obtained using an appropriate method. Tumor tissue should be submitted as a newly acquired excisional or core needle (minimum 18 gauge) or surgical biopsy in formalin. Cytological or fine-needle aspiration, bone specimens are not acceptable. If additional tumor biopsies are collected as part of clinical care, they should be submitted, along with pathology reports, for further analysis. See the Laboratory Manual for details regarding sample handling. At the time of tissue collection process, due diligence should be used to make sure that the tumor sample (not a normal adjacent tissue sample or a tumor margin sample) is provided and contains tumor cells prior to shipment to the central laboratory. This will help ensure that a quality biopsy sample has been taken.

The pathology report accompanying archival tissue may also be requested. The pathology report must be coded with the patient number. Personal identifiers, including the patient's name and initials, must be removed from the institutional pathology report prior to submission. Lilly has a right to retain a portion of the submitted tissue, Archival blocks will be sectioned and returned to the study site. Slides and tissue samples collected on-study will not be returned.

Samples will be retained at a facility selected by Lilly for a maximum of 15 years after the last patient visit for the study, or for a shorter period if local regulations and/or ERBs/IRBs impose shorter time limits. This retention period enables the use of new technologies, response to questions from regulatory agencies, and investigation of variable response that may not be

observed until later in the development of LY3434172 or after LY3434172 becomes commercially available.

Technologies are expected to improve during the 15-year storage period and therefore cannot be specifically named. Existing approaches, including but not limited to mutation profiling, copy number variability analysis, gene expression assays, multiplex assays, and/or immunohistochemistry may be performed on these tissue samples to assess potential associations between these biomarkers and clinical outcomes.

### **9.8.2. Other Samples for Biomarker Research**

The following samples for biomarker research will be collected for the purposes described in Section 9.8, and as specified in [Appendix 4](#), where local regulations allow.

- Whole blood
- Serum
- Plasma
- Stool (when applicable, stool specimens may be collected for microbiome analyses)
- A maximum of 5 samples may be collected at additional time points during the study, if warranted and agreed upon by the investigator and Lilly. If these additional samples are requested, they will be used to further investigate biomarkers that may explain treatment response and resistance mechanisms.

All samples will be coded with the patient number. These samples and any data generated can be linked back to the patient only by the study site personnel.

Samples will be retained at a facility selected by Lilly for a maximum of 15 years after the last patient visit for the study, or for a shorter period if local regulations and/or ERBs/IRBs impose shorter time limits. This retention period enables use of new technologies, response to questions from regulatory agencies, and investigation of variable response that may not be observed until later in the development of LY3434172 or after LY3434172 becomes commercially available.

Technologies are expected to improve during the 15-year storage period and therefore cannot be specifically named. Existing approaches, including but not limited to flow cytometry, mutation profiling, copy number variability analysis, gene expression assays, multiplex assays may be performed on these samples to assess potential associations between these biomarkers and clinical outcomes.

## **9.9. Health Economics**

Health economics and medical resource utilization parameters will not be evaluated in this study.

## 10. Statistical Considerations

### 10.1. Sample Size Determination

The primary objective of this study is to assess the safety and tolerability of LY3434172, thereby identifying and confirming the RP2D of LY3434172 to be administered as monotherapy to patients with solid tumors. The secondary objective is to evaluate PK and any observed evidence of clinical efficacy.

The total sample size in Cohorts A1 to A5/A6 will be determined by the incidence of DLTs. The RP2D could be chosen after the corresponding Q2W cohorts have been enrolled. After the DLT period (Cohorts A1 to A5/A6) is completed, an additional 12 to 15 patients at two dose levels selected from these cohorts will be enrolled for adequate assessment of safety and exploration of PK and pharmacodynamic effects. In parallel, patients will be enrolled in Q3W cohorts (A7 and A8) to allow flexibility for future combinations with standard-of-care agents. The sample size of Q3W depends primarily on PK profiles and clinical considerations.

### 10.2. Populations for Analyses

The following analysis sets will be defined for this study.

**Enrolled/Safety population:** will include all patients who received any quantity of study treatment, regardless of their eligibility for the study. The safety and efficacy evaluation will be performed based on the first dose of study treatment a patient actually received. This population will be used for all dosing/exposure, safety, and efficacy analyses.

**Pharmacokinetic analysis set:** will include all enrolled patients who received at least one dose of LY3434172 and have at least one evaluable PK sample.

**Biomarker analysis set:** will include the subset of enrolled patients from whom a valid assay result has been obtained. No imputation will be performed for missing data due to the limitation of small sample size.

### 10.3. Statistical Analyses

Statistical analysis of this study will be the responsibility of Lilly or its designee.

Unless otherwise stated, all confidence interval (CIs) will be given at a 2-sided 95% level.

Any change to the data analysis methods described in the protocol will require an amendment only if it changes a principal feature of the protocol. Any other change to the data analysis methods described in the protocol, and the justification for making the change, will be described in the Statistical Analysis Plan (SAP) and clinical study report (CSR). Additional exploratory analyses of the data will be conducted as deemed appropriate.

#### 10.3.1. Safety Analyses

All patients who receive any quantity of LY3434172 will be evaluated for safety and toxicity. Severity grades will be assigned by the investigator using CTCAE Version 5.0.

Safety analyses will include summaries of the following:

- DLTs: the number of patients who experience any DLTs during Cycle 1 will be summarized by cohort by treatment arm
- DLT-equivalent: the number of patients who experience any AE that qualifies as a DLT during any period of study will be summarized by the first dose by treatment arm and by tumor type
- AEs, including severity and possible relationship to study drug
- AEs by Medical Dictionary for Regulatory Activities system organ class (SOC) by decreasing frequency of Preferred Term within an SOC
- laboratory and non-laboratory AEs by CTCAE Version 5.0 term, maximum CTCAE grade, and CTCAE Grade 3 and above (regardless of causality and at least possibly related to study treatment)
- changes in vital signs and ECGs

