### 7.2.1. Selection and Timing of Doses

The doses will be administered at approximately the same times on each day. The actual time of all dose administrations will be recorded in the electronic case report form (eCRF).

A cycle is defined as an interval of 28 days (Q2W regimen) and 21 days (Q3W regimen) as shown in [Table JZEA.7](#). A delay of a cycle due to holiday, weekend, bad weather, or other unforeseen circumstances will be permitted for a maximum of 7 days and not counted as a protocol deviation. The reason for the delay should be documented on the eCRF.

The first study treatment will be administered within 7 days after the patient is assigned to a treatment cohort. There should be a minimum of 14 days between doses of study drug for all cohorts in Q2W schedule and 21 days between doses of study drug for the Q3W schedule. However, if there is a delay due to holiday, weekend, bad weather, or other unforeseen circumstances, a flexibility of  $\pm 3$  days is permitted.

A patient may continue to receive LY3434172 until he or she meets one or more of the specified reasons for discontinuation (see Section 8).

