### 7.2.2.2. Dose-Limiting Toxicity Determination

A DLT is defined as any of the events listed in [Table JZEA.8](#), if both the following criteria are met:

- the event occurs during the DLT observation period (Cycle 1, 42 days) for Cohort A1, (Cycle 1, 28 days) for Cohorts A2 to A5 (A2 to A6 if Cohort A6 is opened), (Cycle 1 and 2, 42 days) for Cohorts A7 and A8, and
- the event is clinically significant and definitely, probably, or possibly related to LY3434172, in the opinion of the investigator.

Patients in Cohorts A1 to A5/6, A7, and A8 who experience a DLT in Cycle 1 will be discontinued from study treatment.

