#### **7.2.2.2 DLT-Equivalent Toxicities**

A DLT-equivalent toxicity (ET) is an AE that meets the DLT criteria as defined above and occurs in any cycle other than the DLT assessment period (28 days for Q2W schedule and 42 days for Q3W schedule). In addition to the DLT assessment period, available safety data beyond the DLT assessment period may also be taken into consideration prior to a decision to advance to the next dose level or the determination of the RP2D.

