### **6.12.2. Dose-Limiting Toxicities and DLT-Equivalent Toxicities**

Definitions of DLTs and DLT-equivalent toxicities (DETs) are provided in Section 7.2.2.2 of Protocol JZEA.

Dose-limiting toxicities will be summarized and listed for the DLT-evaluable population (defined in Section 7.6.1 of Protocol JZEA), and DETs will be listed and summarized for the safety population.

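### Protocol 10.3.1 counts DLTs in Cycle 1 only, which covers 21 of the 42 DLT days in Cohorts A7/A8 and leaves Cohort A1 ambiguous

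*Protocol*

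**What the plan says.** DLTs head the list of primary endpoints (Protocol Table JZEA.6). Protocol 10.3.1 has two bullets on them. The first reads "DLTs: the number of patients who experience any DLTs during Cycle 1 will be summarized by cohort by treatment arm". The second, for DLT-equivalents, says that "the number of patients who experience any AE that qualifies as a DLT during any period of study will be summarized".

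The window that makes an event a DLT is set in Protocol 7.2.2.2. It is "Cycle 1 and 2, 42 days) for Cohorts A7 and A8" and "Cycle 1, 42 days) for Cohort A1"; Cohorts A2 to A5/A6 have Cycle 1, 28 days. Protocol 7.2.1 fixes the cycle length: "A cycle is defined as an interval of 28 days (Q2W regimen) and 21 days (Q3W regimen". The DLT-equivalent definition in 7.2.2.2.2 covers an event that "occurs in any cycle other than the DLT assessment period (28 days for Q2W schedule and 42 days for Q3W schedule", with no separate figure for A1.

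SAP 6.12.2 states: "Definitions of DLTs and DLT-equivalent toxicities (DETs) are provided in Section 7.2.2.2 of Protocol JZEA". It adds: "Dose-limiting toxicities will be summarized and listed for the DLT-evaluable population (defined in Section 7.6.1 of Protocol JZEA". Protocol 7.6.1.1, the rule found there, names only A1 to A5 or A6. SAP 6.2.1 has its own DLT-evaluable definition, which covers patients from the whole study but puts Cycle 1 in brackets after the observation period. SAP 5.1 restates the windows with shifted punctuation. The two-cycle, 42-day window stands beside A2 to A6, A1 is followed by both 42 and 28 days, and A7/A8 have no window.

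**The concern.** For Q3W patients Cycle 1 is half of the period in which an event can be a DLT. A table programmed from 10.3.1 would count A2 to A6 over their full 28 days and two doses, but A7/A8 over 21 of 42 days and one dose. Set side by side by cohort, the Q3W schedule could look cleaner than its own DLT definition allows. A second programmer, working from SAP 6.12.2, would count all 42 days and could report a different number for the same patients. At stake is the consistency of the first-listed primary endpoint.

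**Working it through.** **Window lengths.** Inputs: cycle lengths (Protocol 7.2.1), DLT windows (7.2.2.2), visit days (Appendix 4).

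- A7/A8: 2 × 21 = 42 days, which reproduces the plan's figure. Cycle 2 Day 1 is 1 + 21 = day 22 and Cycle 3 Day 1 is 1 + 42 = day 43, as in Appendix 4. Cycle 1 is days 1 to 21. Omitted: days 22 to 42, which is 42 − 21 = 21 days, or 21/42 = 50%. Doses fall on days 1 and 22, so only the first is covered.
- A1: 42/28 = 1.5 cycles, so 42 days cannot be one Q2W cycle. If Cycle 1 ends on day 28, days 29 to 42 are omitted: 14 days, 14/42 = 33%. If Cycle 1 is a label for the window, none are.
- A2 to A5/A6: the window and the cycle are both 28 days, so the protocol count omits nothing.

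**Where an event that meets the DLT criteria lands**

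| Event | DLT by 7.2.2.2 | 10.3.1 DLT count | DLT-equivalent by 7.2.2.2.2 | 10.3.1 DLT-equivalent summary | DLT under SAP 6.12.2 |
|---|---|---|---|---|---|
| A7/A8, day 30 | Yes | No | No | Yes | Yes |
| A1, day 35 | Yes | No on a 28-day cycle; yes if Cycle 1 labels the window | Yes on the 28-day figure | Yes | Yes |
| Any cohort, day 10 | Yes | Yes | No | Yes | Yes |

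The last row shows that the second bullet takes in every DLT, so the two summaries overlap in all cohorts.

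**Evaluable population.** An A7/A8 patient who completes Cycle 1 and has a DLT on day 30 is in the SAP 6.2.1 population. The bracketed Cycle 1 therefore does not remove the event. Taken literally, it does admit a patient who completes Cycle 1 without a DLT and leaves on day 25, after 25 of 42 days. Protocol 7.6.1.1, to which SAP 6.12.2 points, has no rule that names A7/A8.

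**Illustration only.** Assume a 42-day risk p of a first DLT and a cumulative hazard proportional to t^k, with k = 0.5 (front-loaded), 1 (constant) or 2 (rising). Then:

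- risk by day 21: r = 1 − (1 − p)^(0.5^k)
- share of patients missing from the count: q = p − r
- chance that at least one of three patients is missing: 1 − (1 − q)³ (three is the cohort minimum in Protocol 5.2)

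For p = 0.30 and k = 1: r = 1 − 0.70^0.5 = 0.1633, q = 0.1367, and 1 − 0.8633³ = 0.357.

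| p | q at k = 0.5 / 1 / 2 | At least one of three missing |
|---|---|---|
| 0.30 | 0.0771 / 0.1367 / 0.2147 | 21% / 36% / 52% |
| 0.20 | 0.0540 / 0.0944 / 0.1457 | 15% / 26% / 38% |
| 0.10 | 0.0282 / 0.0487 / 0.0740 | 8% / 14% / 21% |

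The 30% case is the target rate in Protocol 7.2.2.1. Q3W doses are matched in exposure to Q2W levels that have cleared the DLT period (5.1.1, 5.2), so lower rates are plausible.

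**The case against.** The strongest reply is that the intent is clear. Protocol 7.2.2.2 defines the windows, and SAP 6.12.2 adopts that definition with no Cycle 1 limit. This stands. A reader might infer that the SAP also drops days 22 to 42, but the documents do not support that: the bracketed Cycle 1 in SAP 6.2.1 says who is evaluable, not which events count.

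Second, the protocol uses Cycle 1 as shorthand for the DLT window, in 7.4 and in the 42-day A1 window itself. For A1 this stands, and it is why the A1 omission, and the overlap with the DLT-equivalent definition, can only be called ambiguous. It does not rescue A7/A8, because 7.2.2.2 names Cycle 2 as well as Cycle 1 for those cohorts.

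Third, nothing is lost. The second bullet of 10.3.1 covers all periods, DLT-equivalents are also a listed primary safety endpoint, and SAP 6.12.3 lists every AE with its dates. This stands too. But that summary mixes all periods and is arranged by first dose, treatment arm and tumor type, and 7.2.2.2.2 says that an A7/A8 event inside 42 days is not a DLT-equivalent.

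Fourth, a reader might infer that escalation or the RP2D would rest on a truncated count. The documents do not show this. Section 10.3.1 is a reporting rule, the DLT definition is the one in 7.2.2.2, and 7.2.2.2.2 lets safety data from beyond the DLT period inform dose decisions.

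**Conclusion.** The defect is real and limited to reporting. As written, the protocol's DLT count covers 21 of 42 days for A7/A8, and 28 or 42 of 42 days for A1 depending on how Cycle 1 is read. The A7/A8 figure rests only on 7.2.1, 7.2.2.2 and 10.3.1. The SAP supports the full window for the event count. Its remaining faults are the evaluable-population label, a cross-reference to a rule that omits A7/A8, and the misplaced windows in SAP 5.1. That last fault also touches A2 to A6 at SAP level, although their count under the protocol is unaffected.

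The percentages in the illustration are not estimates of what will happen. The documents give no DLT timing or rate for these cohorts, and the figures show only how often a patient would move from one summary to another under assumed rates and hazard shapes. The point should be fixed before the DLT tables are programmed, because the count concerned is a primary endpoint.

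**What to change.** 1. Protocol 10.3.1, first bullet: replace 'during Cycle 1' with *during the cohort-specific DLT observation period in Section 7.2.2.2*.
2. Protocol 10.3.1, second bullet: replace 'during any period of study' with *outside the cohort-specific DLT observation period*. For analysis, use that same window in place of the 28/42-day wording of 7.2.2.2.2. Each event is then counted once.
3. SAP 6.2.1: replace the bracketed Cycle 1 with the same reference and, for analysis only, apply the DLT-evaluable definition to A7/A8 over their 42-day window. Patient replacement under Protocol 7.6.1.1 stays as it is.
4. SAP 5.1: correct the list of windows to match Protocol 7.2.2.2.

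The sponsor should also reconcile the other passages that tie the DLT window to Cycle 1: the last sentence of Protocol 7.2.2.2, Section 7.4 and Section 8.1. No clinical rule is proposed for them here.

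The cost is wording only: no added data, visits or patients. Protocol 10.3 allows analysis changes that do not alter a principal feature to be described in the SAP and the study report; whether this one qualifies is for the sponsor to decide. SAP 5.1 needs revision anyway, since it still confines the added patients to A4 and A5/6, while Protocol 5.1 now allows A1 to A5/6.

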### 7.6.1. *Evaluable Patients*

#### 7.6.1.1 DLT-Evaluable Patients in Phase 1 Dose Escalation

Dose escalation refers to Cohort A1 to A5 or Cohort A1 to A6 (if Cohort A6 is opened).

A patient will be DLT evaluable if he or she experiences a DLT during the DLT observation period and has received at least one dose of study drug.

If a patient does not experience a DLT during the DLT observation period, he or she will be DLT evaluable if he or she receives all assigned doses of study drug(s) during the DLT observation period

Patients who receive all doses of study drug but discontinue from study treatment before the end of the DLT observation period will be considered DLT evaluable for the assessment of a dose level, provided it can be documented that the patient did or did not experience a DLT within the DLT observation period.

Patients who are not DLT evaluable may be replaced to ensure that enough patients complete the DLT observation period at each dose level, unless accrual to that cohort has stopped due to a DLT.

A patient may be deemed non-evaluable for assessment of a dose level in the event the patient experiences an AE which would meet DLT criteria, and furthermore has been determined through discussion between investigator and Lilly CRP/CRS to most likely be related to a concomitant medication or a prior line of immune therapy (in the case of irAEs) due to previously established linkage.

To ensure collection of adequate PK or biomarker data, patients who complete the DLT observation period but who do not have a valid PK or biomarker assay result may be replaced, upon consultation with the investigator(s) and the Lilly CRP/CRS, unless accrual to that cohort has stopped because of a DLT. Patients who are replaced for purposes of the PK or biomarker analysis are still considered DLT evaluable.

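### Cohorts A7/A8 have a 42-day DLT window, but the protocol's DLT count and DLT stopping rule cover only Cycle 1, which is 21 days and one of two doses

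*Protocol*

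**What the plan says.** **Window.** Protocol 7.2.2.2 sets the DLT window by cohort: "DLT observation period (Cycle 1, 42 days) for Cohort A1", 28 days for A2 to A5/A6, and for the Q3W cohorts "Cycle 1 and 2, 42 days) for Cohorts A7 and A8". Section 7.2.1 fixes the cycle length: "A cycle is defined as an interval of 28 days (Q2W regimen) and 21 days (Q3W regimen").

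**Count.** Protocol 10.3.1 says "the number of patients who experience any DLTs during Cycle 1 will be summarized by cohort by treatment arm", with no exception for Q3W. Its next bullet, on DLT-equivalents, covers "the number of patients who experience any AE that qualifies as a DLT during any period of study". Section 7.2.2.2.2 (DLT-Equivalent Toxicities) is narrower: a DLT-equivalent meets the DLT criteria and "occurs in any cycle other than the DLT assessment period (28 days for Q2W schedule and 42 days for Q3W schedule").

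**Stopping.** The last sentence of 7.2.2.2 reads "Patients in Cohorts A1 to A5/6, A7, and A8 who experience a DLT in Cycle 1 will be discontinued from study treatment". The matching criterion in Section 8.1 also ties the DLT to Cycle 1. It then adds DLT-equivalents and a residual category for unacceptable toxicity.

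**Denominator.** SAP 6.12.2 takes its event definitions from protocol 7.2.2.2 and its DLT-evaluable population from protocol 7.6.1. The only definition there, 7.6.1.1, is headed for dose escalation and opens "Dose escalation refers to Cohort A1 to A5 or Cohort A1 to A6 (if Cohort A6 is opened"). It requires a patient without a DLT to have had every assigned dose in the window. SAP 6.2.1 gives its own definition. That one covers all study patients, labels the window Cycle 1, admits patients who discontinue with a documented DLT assessment, and has no dose requirement.

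**The concern.** DLTs are the first-listed primary endpoint. Cycle 1 is a correct label for A2 to A6, where cycle and window are both 28 days. It is wrong for A7/A8, for which 7.2.2.2 itself names two cycles. The part left out is the part that follows the second dose. Section 7.4 expects immune-related events either soon after the first dose or months after the last, so days 22 to 42 cannot be assumed free of events. Section 5.2 allows cohorts of three, so one event placed in or out of the table moves the reported proportion by a third. The label also sits in the stopping rules, so the question affects patient management as well as tabulation.

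**Working it through.** **1. Reproduce the stated window.** Two Q3W cycles × 21 days = 42 days, as 7.2.2.2 states. Doses at 21-day spacing fall on days 1 and 22. Appendix 4 agrees: it places C2D1 on day 22 and C3D1 on day 43.

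**2. Share covered by Cycle 1 in A7/A8.** Days: 21/42 = 50%. Doses: 1 of 2 (day 1 only).

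**3. Follow one event through the rules.** Take three evaluable A7 patients, one of whom has a DLT on day 30 (30 > 21, 30 ≤ 42).

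| Rule | Treatment of the event | Result |
|---|---|---|
| Protocol 7.2.2.2 | Inside the 42-day window | DLT, 1 of 3 |
| Protocol 10.3.1, DLT bullet | Outside Cycle 1 | 0 of 3 |
| Protocol 10.3.1, DLT-equivalent bullet | Any period counts | Shown there |
| Protocol 7.2.2.2.2 | Inside the 42 days, so excluded | Not a DLT-equivalent |
| SAP 6.12.2 | Uses 7.2.2.2, no Cycle 1 limit | DLT, 1 of 3 |
| Protocol 8.1, toxicity criterion | Neither a Cycle 1 DLT nor a DLT-equivalent | Residual category only |

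The DLT count is 0 of 3 or 1 of 3 according to the sentence followed. The DLT-equivalent bullet does not reconcile them: it puts the event in another table, contrary to the definition in 7.2.2.2.2.

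**4. Cohort A1.** Its 42-day window is labelled Cycle 1, but a Q2W cycle is 28 days and Appendix 4 places C2D1 on day 29. If Cycle 1 means 28 days, the count covers 28/42 = 67% of the window and 2 of 3 doses (days 1 and 15, not 29). If it means the 42 days that 7.2.2.2 attaches to it, nothing is lost. Separately, 7.2.2.2.2 gives 28 days for all Q2W cohorts, so an A1 event on days 29 to 42 is a DLT under 7.2.2.2 and also a DLT-equivalent.

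**5. Evaluable definitions.** Compare SAP 6.2.1 with protocol 7.6.1.1 read over 42 days, for Q3W patients without a DLT:
- Stops on day 10 with a documented no-DLT assessment: included by 6.2.1 through its discontinuation route; excluded by 7.6.1.1, because dose 2 was not given.
- Skips dose 2 but stays under observation to day 42: included by 6.2.1; excluded by 7.6.1.1.

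Both differences come from the all-doses rule. They would remain if Cycle 1 in SAP 6.2.1 were simply changed to 42 days, so the two definitions need reconciling in their own right.

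**The case against.** The strongest reply is that the SAP already has the right rule. SAP 6.12.2 points to 7.2.2.2, adds no Cycle 1 limit, and so counts the day-30 event. Protocol 10.3 also allows analysis changes that do not alter a principal feature to be made in the SAP and the clinical study report. This stands as a reason why loss is not certain. It does not settle the conflict. Protocol 10.3 asks for such changes to be described and justified, and the SAP describes no departure from 10.3.1. SAP 6.2.1 itself labels the window Cycle 1.

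A reader might infer three stronger things that the documents do not support:
- **That late Q3W DLTs vanish.** They remain in the AE summaries, cohort safety reviews and RP2D discussion, and 7.2.2.2.2 allows safety data beyond the window to be considered.
- **That A7/A8 have no denominator.** SAP 6.2.1 covers every study patient. In 7.6.1.1 the sentence naming A1 to A6 defines dose escalation, while the sentences that define an evaluable patient name no cohort. The defect is two unequal definitions.
- **That dose decisions would go wrong.** Cohort reviews look for DLTs, which 7.2.2.2 defines over 42 days here. The Q3W doses are chosen to match the exposure of selected Q2W levels, and the Q3W sample size depends mainly on PK and clinical considerations.

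On stopping, the residual category and investigator discretion in 8.1, with the toxicity tables in 7.4, would probably lead to discontinuation in many such cases. What is missing is the automatic stop that the protocol intends for a DLT.

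**Conclusion.** The concern holds as a conflict of rules on a primary endpoint. For A7/A8, the protocol's DLT count covers half the days and one of the two doses in the window that the protocol defines. One DLT after dose 2 in a cohort of three is reported as 0 of 3 or 1 of 3 depending on the rule followed. The DLT stopping rules have the same limit. The A1 labelling is an ambiguity, with a loss only on the 28-day reading.

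This rests on the literal text and on the cycle lengths in 7.2.1. How many events would be affected cannot be estimated, because the documents give no DLT onset times. It should be corrected, but it does not threaten the trial's safety data as a whole.

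**What to change.** - In protocol 10.3.1, protocol 8.1, the last sentence of protocol 7.2.2.2, and SAP 6.2.1, replace Cycle 1 with: the cohort's DLT observation period (Section 7.2.2.2).
- State that 7.6.1.1 applies to A7/A8 over 42 days, and make SAP 6.2.1 refer to it as the single DLT-evaluable definition.
- In 7.2.2.2.2, give A1 its 42-day window, so that DLT-equivalents are events outside each cohort's own window.
- Correct the misplaced punctuation in the list of windows in SAP 5.1. This is clerical.

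Section 7.4 also labels the window Cycle 1 in its ban on dose modification. That should be decided separately, because extending the label there would extend the ban to dose 2.

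The cost is wording only: no new data, and no change to the Appendix 8 decision table. The stopping-rule edits belong in a protocol amendment. There are two consequences to accept. A Q3W patient without dose 2 and without a DLT leaves the evaluable denominator of a cohort that may hold three patients. A Q3W DLT on days 22 to 42 becomes an explicit reason to stop treatment.
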